5.2. Determination of Sample Size

Approximately 42 patients will be randomized in order that approximately 36 patients complete the study.

Assuming that a standard deviation (SD) of between-period differences of 10% and a 2-sided alpha level of 0.10, 36 completers will provide approximately 90% power to detect a 5% difference between LY900014 and Humalog, in the percentage of time with SG (Sensor Glucose) values from 70 to 180 mg/dL (inclusive), during the last 2 weeks of each 4-week treatment period.

Assuming a 12% dropout rate after randomization, approximately 42 patients (21 patients in each sequence) will need to be randomized.

5.3. Method of Assignment to Treatment

Patients who meet all criteria for enrollment and complete the lead-in period will be randomized to double-blind treatment at Visit 4. Assignment to treatment sequences will be determined by a computer-generated random sequence using an interactive web-response system (IWRS).

Patients will be randomized to 1 of the 2 treatment sequences in a 1:1 ratio:

Sequence A: LY900014 → Humalog

Sequence B: Humalog → LY900014

Stratification will be by hemoglobin A1c (HbA1c) stratum ($\leq 7.0\%$, $> 7.0\%$ at Visit 1) and percentage of time with SG values from 70 to 180 mg/dL over the 2 weeks prior to randomization ($\leq 75\%$, $> 75\%$).

Patients will begin using a new reservoir and infusion set prior to leaving the investigative site at Visits 2, 4, 7, and 10. Patients will change the pump reservoir and infusion set every 3 days unless a change is required due to failure of the infusion set.

The IWRS will be used to assign all study treatment during the study, including Humalog during the lead-in period. The IWRS will be used to assign vials containing double-blind investigational product (IP) to each patient randomized to the sequence of treatments. Site personnel will confirm that they have located the correct vials by entering a confirmation number found on the vials into the IWRS.

6. A Priori Statistical Methods

6.1. General Considerations

Statistical analysis of this study will be the responsibility of Lilly or its designee. Any change to the data analysis methods described in the protocol will require an amendment ONLY if it changes a principal feature of the protocol. Any other change to the data analysis methods described in the protocol, and the justification for making the change, will be described in the SAP or the clinical study report (CSR). Additional exploratory analyses of data will be conducted, as deemed appropriate.

For purposes of analysis, the following populations are defined in [Table ITSM.6.1](#):

Table ITSM.6.1. Patient Populations

Population	Description
Entered	All patients who give informed consent.
Enrolled	All patients who receive at least 1 dose of open-label Humalog in the 2-week lead-in period.
Randomized	All patients who are randomly assigned to study treatment at Visit 4 and receive at least 1 dose of the randomly assigned IP. Treatment will be defined on the basis of the treatment the patients are assigned to.
Pilot	All patients in the pilot safety assessment.

Unless otherwise specified, all efficacy and safety analyses will be conducted on the Randomized Population. Analyses of adverse events (AEs) will include all data collected during the course of the entire 4-week treatment period for each treatment regardless of IP use. Analyses of hypoglycemia and CGM measures will be conducted using the data from first dose to last dose of IP in each 4-week treatment period, and due to the crossover design, treatment comparisons will be based upon the derived outcome variables for Week 2 to 4 in each 4-week treatment period. Analyses of the CareLink report data that are transferred to eCRF (eg, percentage of time spent in Auto Mode, total daily doses during the last 2 weeks) will include all data collected, regardless if patients are temporarily off pump or IP during the 2 weeks or not. Pump-related safety analyses (eg, infusion set changes) will exclude data (if any) that are collected while patients are temporarily off pump or off IP. For analyses of CGM, insulin doses and meal information by infusion set wear day, only data from the infusion sets with ≥ 60 hours (2.5 days) of wear will be included so that adequate data can be used for by-day (Day 1, Day 2, and Day 3) comparison. Data collected during the safety follow-up period will not be used for comparisons between treatments.

Unless otherwise noted, all tests of treatment effects will be conducted at a 2-sided alpha level of 0.10, and confidence intervals (CIs) will be calculated at 90%, 2-sided.

Treatment comparisons will be performed for the primary objective (Section 6.9.1) at the full significance level of 0.10. No multiplicity adjustment will be made for secondary and exploratory objectives.

The definitions of baseline and post-baseline for the safety and efficacy analyses depend on which analysis period is being used. The following analysis periods will be used:

- Lead-in Period – from after Visit 2 to Visit 4
- 4-Week of Each Randomized Treatment Period while on IP – from first dose to last dose of IP in each 4-week randomized treatment period (Period I and Period II)
- 4-Week of Each Randomized Treatment Period Regardless of IP use – from the beginning to the end of each 4-week randomized treatment period (including all data regardless of IP use)
- Week 2 to 4 of Each Randomized Treatment Period while on IP – last 2 weeks of each 4-week randomized treatment period before the last dose of IP
- Week 2 to 4 of Each Randomized Treatment Period Regardless of IP – last 2 weeks of each 4-week randomized treatment period (including all data regardless of IP use)
- Safety Follow-up Period – Visit 801

Table ITSM.6.2 describes the rules for determining the patient population, baseline, and postbaseline observations for the different analysis periods. The data in the lead-in and the safety follow-up visit, if summarized, will be for overall, not by treatment.

The data on IP is defined based on the following rules:

- for data only measured at an office visit (eg, HbA1c and 1,5 Anhydroglucitol [1,5-AG]), if the office visit date (or laboratory sample collection date) is within 14 days of the date of last study drug dose of the current randomized treatment period (Period I or Period II), then postbaseline data measured at or prior to that office visit will be considered as data on IP for the current randomized treatment period.
- for data collected as running records with an exact date and/or time stamp such as hypoglycemia entries where the date and time of the measures is not tied with the date of an office visit, postbaseline data with date and time \leq (last study drug dose date and time) will be considered as data on IP for the current randomized treatment period.

For continuous measures, summary statistics will include sample size, mean, SD, median, minimum, and maximum for both the actual and the change from baseline measurements. Least squares (LS) means and standard errors derived from the analysis models will also be displayed for the change from baseline measurements. Treatment comparisons will be displayed showing the treatment difference LS means and the 90% CIs for the treatment differences, along with the p-values for the treatment comparisons.

Unless otherwise specified, a restricted maximum likelihood based, mixed-effect model repeated measures (MMRM) analysis will be used to analyze continuous longitudinal variables. The longitudinal observations for both treatment periods will be included in the analysis. The model will include the fixed class effects of treatment, period, sequence, strata (HbA1c [$\leq 7.0\%$, $>7.0\%$] and percentage of time with SG values from 70 to 180 mg/dL over the 2 weeks prior to randomization [$\leq 75\%$, $>75\%$]), and the continuous, fixed covariate of baseline value. The

Kenward-Roger approximation will be used to estimate denominator degrees of freedom. An unstructured covariance structure will be used to model the within-patient errors. If this analysis fails to converge, a covariance structure of compound symmetry without heterogeneous variances will be used. If the model still does not converge, strata may be removed from the model. Significance tests will be based on LS means and Type III tests. SAS PROC MIXED will be used to perform the analysis.

For categorical measures (such as incidence of AEs), summary statistics will include sample size, frequency, and percentages. Prescott's exact test will be used for treatment comparisons, unless otherwise specified. Since Prescott's exact test is essentially a Fisher's exact test on the preference score and treatment sequence, if all events occurred in the same treatment sequence, p-values from Prescott's test will not be calculated.

For laboratory values, both conventional (CN) and Systeme International (SI) units will be presented. Therefore, both % and mmol/mol will be presented for HbA1c and both mg/dL and mmol/L will be presented for glucose measurements.

Table ITSM.6.2. Baseline and Post-Baseline Definitions and Patient Population by Study Period and Type of Analysis

Study Period/Analysis	Patient Population	Baseline Observations	Post-Baseline Observations
Lead-In Period (Overall^a only)			
TEAEs	Enrolled Population	Prior to first dose of open-label Humalog (or Visit 2 date if the dose date is missing)	The entire lead-in period after first dose of open-label Humalog and prior to first dose of IP (or Visit 4 date if the dose date is missing)
4-Week of Each Randomized Treatment Period While on IP (from first to last dose of IP in each 4-week randomized treatment period)			
Unplanned infusion set changes by reason (pump occlusion alarm; unexplained high BG; infusion site reaction (pain, redness or swelling at infusion site), or infusion set problem (infusion set kinked, pulled out, leaking, reservoir empty, etc.))	Randomized Population	From first to last dose of open-label Humalog, excluding data (if any) that are collected while patients temporarily are off pump or off open-label Humalog	From first to last dose of IP in each randomized treatment period (Period I and Period II), excluding data (if any) that are collected while patients temporarily are off pump or off IP

Baseline and Post-Baseline Definitions and Patient Population by Study Period and Type of Analysis

Study Period/Analysis	Patient Population	Baseline Observations	Post-Baseline Observations
Time interval until infusion set change	All patients in the Randomized Population with a baseline and a post-baseline observation	From first to last dose of open-label Humalog, excluding data (if any) that are collected while patients temporarily are off pump or off open-label Humalog	From first to last dose of IP in each randomized treatment period (Period I and Period II), excluding data (if any) that are collected while patients temporarily are off pump or off IP
Hypoglycemia events	Randomized Population	From first to last dose of open-label Humalog	Visits 4, 5, 6, 7, 8, 9 and 10 that fall between first and last dose of IP in each randomized treatment period (Period I and Period II). More detailed analysis period can be found in Section 6.10.4.
HbA1c summary statistics	All patients in the Randomized Population with a baseline and at least one post-baseline observation while on IP	Last value of Visits 1-4 prior to or on the date of the first dose of IP	Visits 7 and 10 while on IP ^d
1,5-AG	All patients in the Randomized Population with a baseline and at least one post-baseline observation while on IP	Visit 4 prior to or on the date of the first dose of IP	Visits 7 and 10 while on IP
Pump factors - CR, ISF, and AIT ^b	All patients in the Randomized Population with a baseline and at least one post-baseline observation	Last value of Visits 2-4 prior to or on the date of the first dose of IP	Last observation 1 day prior to Visit 7 and last observation 1 day prior to Visit 10 prior to last dose in IP of each randomized treatment period (Period I and Period II) excluding data (if any) that are collected while patients temporarily are off pump or off IP

Baseline and Post-Baseline Definitions and Patient Population by Study Period and Type of Analysis

Study Period/Analysis	Patient Population	Baseline Observations	Post-Baseline Observations
4-Week of Each Randomized Treatment Period Regardless of IP use (from randomization to Week 4 of each randomized treatment period regardless of IP use)			
TEAEs	Randomized Population	Prior to first dose of randomized IP (or Visit 4 if the dose date is missing)	Each 4-week randomized treatment period regardless of IP use
Weight and vital signs	All patients in the Randomized Population with a baseline and a post-baseline observation	Last of Visits 2-4	Visits 7 and 10 regardless of IP use
Week 2-4 of Each Randomized Treatment Period while on IP			
CGM outcome variables	All patients in the Randomized Population (with a baseline and a post-baseline observation for continuous variables, unless otherwise specified ^c)	From first to last dose of open-label Humalog, excluding data (if any) that are collected while patients temporarily are off pump or off open-label Humalog	From first to last dose of IP in each randomized treatment period (Period I and Period II), excluding data (if any) that are collected while patients temporarily are off pump or off IP
Week 2-4 of Each Randomized Treatment Period Regardless of IP			
Basal, bolus, and total insulin doses, bolus/total insulin dose ratios ^d	All patients in the Randomized Population with a baseline and a post-baseline observation	Last of Visits 2-4	Visits 7 and 10 regardless of IP use
Basal, bolus, and total insulin doses, bolus/total insulin dose ratios by infusion set wear day, by meal, and by infusion set wear day and meal ^e	All patients in the Randomized Population with a baseline and a post-baseline observation	Last of Visits 2-4	Last observed value before/at Visit 7 and before/at Visit 10 regardless of IP use
Percentage of time (per week) spent in Auto Mode ^f	All patients in the Randomized Population with a baseline and a post-baseline observation	Last of Visits 2-4	Visits 7 and 10 regardless of IP use
Safety Follow-Up Visit (Overall^a Only)			
TEAEs	All patients in the Randomized Population who enter the safety follow-up period	Prior to first dose of randomized IP (or Visit 4 if the dose date is missing)	From the date of the last visit of the 8-Week treatment period + 1 day to the end of study
Weight and vital signs	All patients in the Randomized Population who enter the safety follow-up period	Last of Visits 2-4	Visit 801

Abbreviations: 1,5-AG = 1,5-Anhydroglucitol; AIT = active insulin time; BG = blood glucose; CGM = continuous glucose monitoring; CR = carb ratio; eCRFs = electronic case report forms; HbA1c = hemoglobin A1c; IP = investigational product; ISF = insulin sensitivity factor; TEAE = treatment-emergent adverse event.

- a “Overall” means that data will be summarized in total and no by-treatment summary or statistical analysis will be included.
- b The pump settings that patients started with in each treatment period (lead-in, Period I and Period II) are captured in the eCRF. Changes during the study are captured in CareLink raw data. The pump settings that patients ended up within each treatment period will be the last observed value from the two data sources 1 day prior to the last office visit.
- c Not required for the duration of hypoglycemic episode because it is possible that some patients may not have any hypoglycemic event during the lead-in period to be used as baseline values.
- d Mean insulin doses (mean total daily basal and mean total daily bolus) during the last 1 week for Visit 2 and during the last 2 weeks for Visits 4, 7, and 10 from the CareLink report will be entered into eCRFs. These data will be used for summary and analyses of mean total daily basal dose, mean total daily bolus dose, mean total daily insulin dose, and the ratio of mean total daily bolus dose to mean total daily insulin dose.
- e Calculated from the CareLink raw data by adding up all insulin doses that fall into the specified time interval (e.g., a specific infusion set wear day), regardless of whether the pump is in Auto Mode or not.
- f Captured in the eCRF as “percentage of time spent in Auto Mode per week for the past 1 week” at Visit 2 and as “percentage of time spent in Auto Mode per week for the past 2 weeks” at other visits.

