Week of Treatment	-3	-2	-1	0	*	2	4	*	6	8	10	
Visit Window (±days)	0	3	3	3	3	3	3	3	3	3	7	
Study Logistics												
Informed consent signed	X											
Eligibility Criteria Reviewed	X	X										
Randomization				X								
IWRS	X	X	X	X	X	X	X	X	X	X	X	X
Crossover							X					
Clinical Assessments												
Patient demographics	X											
Medical history and preexisting conditions	X											
Physical examination/height	X											
ECG (12-lead) ^b	X											
Body weight	X	X		X			X			X	X	X
Vital signs: blood pressure/pulse rate ^c	X	X		X			X			X	X	X
Concomitant medication	X	X	X	X	X	X	X	X	X	X	X	X
Adverse events		X	X	X	X	X	X	X	X	X	X	X
Patient Education and Management												
Set standardized high/low glucose alerts		X		X			X					
At screening, record pump bolus delivery speed (Standard [1.5 U/min] or Quick [15 U/min]). At other office visits, confirm and record pump bolus delivery speed unchanged from screening.	X	X		X			X			X		
At screening, record infusion set cannula length (6mm or 9mm). If changed during study, record infusion set cannula length (6mm or 9mm) and reason for change.	X	X		X			X			X		
Reset pump ISF, CR, and AIT to randomization settings							X					
Change infusion set and reservoir at investigative site ^d		X		X			X			X ^e		X ^e

	Screening	Lead-In		Study Period I				Study Period II			Safety Follow-up	Early Termination
Visit	1	2	3a	4	5a	6a	7	8a	9a	10	801	ET
Week of Treatment	-3	-2	-1	0	*	2	4	*	6	8	10	
Visit Window (±days)	0	3	3	3	3	3	3	3	3	3	7	
Review/Answer questions on Medtronic 670G System, Diabetes management education, carbohydrate counting, collecting 4-point SMBG profiles, and review hypoglycemia and hyperglycemia management guidelines ^{f,g}		X										
Review total daily insulin dose ^h	X											
Review pump, CGM, and SMBG data for use in clinical decision making		X	X	X	X	X	X	X	X	X		X
Review/discuss hypoglycemia data			X	X	X	X	X	X	X	X	X	X
Remind patient to upload pump data to CareLink weekly		X	X	X	X	X	X	X	X	X		
Ancillary Supplies/Diaries/IP												
Dispense infusion sets, reservoirs, BG test strips, and ancillary supplies		X		X			X			X	X	
Dispense Study Diary		X		X			X			X		
Collect Study Diary and review with patient				X			X			X	X	X
Start open-label Humalog at office visit		X										
Start non-study rapid-acting analog insulin at office visit										X		
Dispense IP				X			X					
Collect used and unused study drug and supplies from patient				X			X			X		X
Transfer Diary Data to eCRF												

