10.3. Statistical Analyses

10.3.1. General Statistical Considerations

Statistical analysis of this study will be the responsibility of Lilly or its designee. Any change to the data analysis methods described in the protocol will require an amendment ONLY if it changes a principal feature of the protocol. Any other change to the data analysis methods described in the protocol, and the justification for making the change, will be described in the statistical analysis plan (SAP) or the clinical study report (CSR). Additional exploratory analyses of data will be conducted, as deemed appropriate.

Unless otherwise specified, all efficacy and safety analyses will be conducted on the Randomized Population. Analyses of AEs will include all data collected during the course of the entire 4-week treatment period for each treatment regardless of IP use. Analyses of hypoglycemia will be conducted from first dose to last dose of IP in each 4-week treatment period. Data collected during the safety follow-up period will only be summarized for overall and will not be used for comparisons between treatments.

Unless otherwise noted, all tests of treatment effects will be conducted at a 2-sided alpha level of 0.10, and confidence intervals (CIs) will be calculated at 90%, 2-sided.

Treatment comparisons will be performed for the primary objective (Section 10.3.3.1) at the full significance level of 0.10. No multiplicity adjustment will be made for secondary and exploratory objectives.

Baseline is defined as the last nonmissing measurement at or before the randomization visit (Visit 4), unless otherwise specified and described in the SAP.

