9. To compare LY900014 and Humalog with respect to the percentage of time with sensor glucose values within range (70 and 140 mg/dL)	9. percentage of time with sensor glucose values between 70 and 140 mg/dL (inclusive), during the last 2 weeks of each 4-week treatment period
10. To compare LY900014 and Humalog with respect to the rate and incidence of unplanned infusion set changes	10. Rate (events/patient/30 days) and incidence of unplanned infusion set changes by reason (Pump occlusion alarm, Suspected infusion set occlusion (unexplained high BG), Infusion site reaction (pain, redness or swelling at infusion site), Infusion set problem (infusion set kinked, pulled out, leaking, reservoir empty, etc.), during the 4-week treatment period
11. To compare LY900014 and Humalog with respect to the percentage of time with sensor glucose values in hyperglycemic glucose ranges	11. Percentage of time with sensor glucose values >180 mg/dL and >250 mg/dL, during the last 2 weeks of each 4-week treatment period

Objectives and Endpoints

Objectives	Endpoints
12. To compare LY900014 and Humalog with respect to the 1-hour postprandial sensor glucose excursions	12. Mean 1-hour postprandial sensor glucose excursions (mean sensor glucose measured 1 hour after the start of the meal minus mean sensor glucose at the start of meal) after breakfast, during the last 2 weeks of each 4-week treatment period
13. To compare LY900014 and Humalog with respect to the within-patient sensor glucose variability	13. Coefficient of variation (CV) (standard deviation/mean) of sensor glucose values, during the last 2 weeks of each 4-week treatment period
14. To evaluate HbA1c of LY900014 and Humalog	14. Summary statistics of actual and change of HbA1c during each 4 week treatment period
15. To evaluate 1,5-AG of LY900014 and Humalog	15. Summary statistics of actual and change of 1,5-AG during each 4-week treatment period
16. To compare LY900014 and Humalog with respect to the factors affecting dosing in pumps	16. Actual and change from baseline in factors affecting dosing in pump (breakfast CR, AIT, breakfast ISF), during the 4-week treatment period

Abbreviations: 1,5-AG = 1,5 Anhydroglucitol; AIT = active insulin time; BG = blood glucose; CR = carb ratio; HbA1c = hemoglobin A1c; ISF = insulin sensitivity factor.

5. Study Design

[figure not shown]

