6.9.2. Other Secondary Efficacy Analyses

The analyses described in Section 6.9.2 will include data collected from the Randomized Population. Details for the CGM analyses are described in Section 6.13.

For the following secondary efficacy endpoints during the last 2 weeks of each 4-week treatment period, an MMRM model similar to that for the primary endpoint will be used:

- actual and change from baseline in insulin doses, including mean total daily basal (U/day, U/kg/day), mean total daily bolus (U/day, U/kg/day), and mean total daily insulin dose (U/day, U/kg/day) and mean total daily bolus /mean total daily insulin dose ratios (%)
- actual and change from baseline in percentage of time (per week) spent in Auto Mode, during the last 2 weeks of each 4-week treatment period
- actual and change from baseline in percentage of time with sensor glucose values <54 mg/dL as measured by CGM

In addition, the longitudinal observations of actual and change during each 4-week treatment period in HbA1c and 1,5-AG will be summarized by period and by treatment sequence. No treatment comparison will be conducted.

To assess the insulin doses over the course of 3 days of continuous infusion, the mean total daily basal and mean total bolus doses during the last 2 weeks of the lead-in and each 4-week treatment period, will be derived based upon the CareLink raw data collected on Day 1, Day 2, and Day 3 of infusion set wear and summarized by treatment. The insulin doses will also be summarized by infusion set wear day, and by both infusion set wear day and meal (0 to 4 hours after the start of meals, excluding data collected after the next meal for the current meal). Only data from the infusion sets with ≥ 60 hours of wear will be included in these doses analyses by infusion set wear day. The treatment comparison will be conducted using an MMRM model similar to that for the primary endpoint.

Before the database lock, it was identified that 1 patient had to replace the pump in the middle of the study and Auto Mode was unavailable for at least 48 hours, and thus data from this patient will be excluded from analysis of percentage of time (per week) spent in Auto Mode.

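### The HbA1c and 1,5-AG change tabulated for Period II is an 8-week change across both insulins, not the 4-week change that the endpoint describes

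*SAP*

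**What the plan says.** SAP Table ITSM.4.1 words endpoint 14 as "Summary statistics of actual and change of HbA1c during each 4 week treatment period" and endpoint 15 as "Summary statistics of actual and change of 1,5-AG during each 4-week treatment period". Protocol Table ITSM.2 words both the same way. SAP 6.9.2 repeats the idea: "the longitudinal observations of actual and change during each 4-week treatment period in HbA1c and 1,5-AG will be summarized by period and by treatment sequence". It then rules out any comparison between treatments for these two variables.

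SAP Table ITSM.6.2 supplies the derivation. The HbA1c baseline is "Last value of Visits 1-4 prior to or on the date of the first dose of IP" and the 1,5-AG baseline is "Visit 4 prior to or on the date of the first dose of IP". Both rows list the same post-baseline observations, "Visits 7 and 10 while on IP". Protocol 10.3.1 likewise places the default baseline at or before Visit 4.

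The protocol's Schedule of Activities puts Visit 1 at week -3, Visit 4 at week 0, Visit 7 at week 4 (the crossover) and Visit 10 at week 8. HbA1c is sampled at Visits 1, 4, 7 and 10, and 1,5-AG at Visits 4, 7 and 10. Both are also taken at early termination.

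**The concern.** The endpoint names a change over one 4-week period. For Period II the table delivers a change over two periods, the first of them on the other insulin. If the result is printed under a Period II heading with the endpoint's wording, the title and the number describe different quantities.

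These summaries are the only planned HbA1c and 1,5-AG results. No model or test elsewhere estimates a within-patient contrast in which a common baseline would cancel, so what the reader learns about change depends on how these tables are derived and labelled.

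**Working it through.** The plan gives no numerical figure for these endpoints to reproduce. The check is the visit calendar applied to the two rows of Table ITSM.6.2.

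**Interval covered by each tabulated change** (nominal weeks from the Schedule of Activities)

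| Change | Weeks | Treatment during the interval |
|---|---|---|
| Visit 7 minus Visit 4 (Period I as tabulated) | 4 - 0 = 4 | Period I insulin |
| Visit 10 minus Visit 4 (Period II as tabulated) | 8 - 0 = 8 | 4 weeks on each insulin |
| Visit 10 minus Visit 7 (within Period II) | 8 - 4 = 4 | Period II insulin |
| Visit 10 minus Visit 1 (HbA1c fallback) | 8 - (-3) = 11 | 3 weeks before randomization, then 4 on each insulin |

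The fallback applies to HbA1c only. Visit 1 is the only scheduled HbA1c sample before Visit 4, and 1,5-AG is not sampled before Visit 4.

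**Can the table be read another way?** The first dose of IP might be taken as the first dose in each period. That does not help, because the eligible visits are limited to 1 to 4 (HbA1c) or 4 (1,5-AG), so Visit 7 cannot qualify. The footnote mark on the HbA1c row leads to a note on insulin doses. No section names Visit 7 as a Period II baseline.

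**How the two changes relate.** Let a = Visit 7 minus Visit 4 and b = Visit 10 minus Visit 7. The tabulated Period II change is a + b. Two cases, using assumed values that are not in the documents:

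- The Period I shift persists: a = -0.10 HbA1c points, b = 0. The tabulated Period II change is -0.10 + 0 = -0.10, all of it arising in Period I. With b = 0 and a anywhere from -0.3 to +0.3, the tabulated figure runs from -0.3 to +0.3 on the same basis.
- The Period I shift reverses: a = -0.10, b = +0.10. The tabulated Period II change is -0.10 + 0.10 = 0, while the within-period change is +0.10.

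The documents do not say which case is closer to the truth for either variable.

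**What can be recovered from the planned tables.** For patients with both visits, the mean of b is the mean Visit 10 change minus the mean Visit 7 change within a sequence. The SD of b cannot be recovered, because it also needs the covariance of the two changes. The subtraction is exact only if both means use the same patients, but the table requires just one post-baseline value. The sample-size section plans for 42 randomized and 36 completers. Up to 42 - 36 = 6 patients could therefore contribute at Visit 7 and not at Visit 10, if all dropouts came after Visit 7.

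**The case against.** The strongest reply is that the phrase about change within each period is loose wording and the derivation is as intended. Protocol 10.3.3.2 uses the same phrase for the secondary variables, and SAP 6.9.2 turns it into change from baseline for insulin doses, Auto Mode time and time below 54 mg/dL. Endpoint 16 combines both expressions. A single baseline before Period I is the SAP's convention for weight, vital signs, pump factors, doses and CGM measures. This stands to the extent that the fault may lie in the wording. But SAP 6.9.2 uses a different phrase for HbA1c and 1,5-AG from the bullets just above it, and on either view the wording and the derivation need to be brought together.

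A second reply is that Visit 7 is not a clean baseline. There is no washout, so Visit 10 minus Visit 7 can include reversal of the Period I effect, as the second case above shows. This stands. It is a reason to keep the pre-randomization baseline and to show the within-period change beside it.

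A reader might infer more: that the plan would present the Period II figure as the effect of the Period II insulin, or that the common baseline is an error which biases a treatment comparison. The documents do not support either. The summaries are by period and by sequence, not by insulin. No comparison is planned. The Period I and Period II results appear together for each sequence, with the actual values. A common pre-randomization baseline is not wrong in a crossover, and the identity a + b does not by itself show bias.

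**Conclusion.** The point holds as a mismatch between an endpoint and its derivation. The change tabulated for Period II spans 8 weeks and both insulins where the endpoint describes 4 weeks, and about 11 weeks for HbA1c in any patient whose only baseline is Visit 1. The Period I change matches the endpoint when the Visit 4 value is present.

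This rests on nominal visit weeks and on the baseline columns of Table ITSM.6.2 being applied as written. It does not depend on any assumed size of effect or carryover.

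Materiality is low. Endpoints 14 and 15 are exploratory and descriptive, and the actual values are reported. The primary analysis and the sample size do not change.

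**What to change.** 1. Keep the pre-randomization baseline in both rows of Table ITSM.6.2, including the fallback to an earlier HbA1c value.
2. Label the Visit 10 result as change from pre-randomization baseline at 8 weeks (both treatments). State how many patients, if any, use a Visit 1 HbA1c baseline.
3. Add the within-period change for Period II, Visit 10 minus Visit 7, with n, mean and SD, by sequence, for patients with both values.
4. Note under the added summary that, with no washout, the change can include reversal of the Period I effect.

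The cost is one added summary per variable, a label and a note. The samples are already scheduled at Visits 4, 7 and 10. Patients without a Visit 7 value drop out of the added summary but remain in the planned one. SAP 6.1 lets a change of this kind be recorded with its justification in the SAP or the clinical study report, because it does not touch a principal feature of the protocol.
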